**Table 2: Scheduled Visit Window and Mapping of Assessments**

Assessment	Scheduled Visit Number	Scheduled Time point	Label on output	Target Study Day*	Time Interval Lower Limit (Day*)	Time Interval Upper Limit (Day*)
laboratory	Baseline	Baseline - Week 1D1	Baseline	1	No Lower limit	1
	Week 2	Week 1D5- Week 3D19	Week 2	15	2	21
	Week 4	Week 4 D22- Week 5 D33	Week 4	29	22	35
	Week 6	Week 6 D36 - Week 6 D40	Week 6	43	36	EOT
	Week 10 Follow-up/ Final visit for withdrawals	Week 10 Follow-up/ Final visit for withdrawals	Week 10 Follow-up/ Final visit for withdrawals	70	EOT+1	No Upper limit
Physical examination, ECG	Baseline	Baseline - Week 1D1	Baseline	1	No Lower limit	1
	Week 6	Week 6 D36 - Week 6 D40	Week 6	43	2	EOT
	Week 10 Follow-up/ Final visit for withdrawals	Week 10 Follow-up/ Final visit for withdrawals	Week 10 Follow-up/ Final visit for withdrawals	70	EOT+1	No Upper limit
Pregnancy test	Baseline	Baseline - Week 1D1	Baseline	1	-24	1
	Week 2	Week 1D5- Week 3D19	Week 2	15	2	21
	Week 4	Week 4 D22- Week 5 D33	Week 4	29	22	EOT
	Week 10 Follow-up/ Final visit for withdrawals	Week 10 Follow-up/ Final visit for withdrawals	Week 10 Follow-up/ Final visit for withdrawals	70	EOT+1	No Upper limit
Questionaries						
ASRS, CAARS-L-SR	Baseline	Baseline - Week 1D1	Baseline	-1	No Lower limit	-1
	Week 2	Week 1D5- Week 3D19	Week 2	15	2	21
	Week 4	Week 4 D22- Week 5 D33	Week 4	29	22	34

	Week 6	Week 6 D36	Week 6 D36	36	35	38
	Week 6	Week 6 D40	Week 6 D40	40	39	EOT
	Week 10 Follow-up/ Final visit for withdrawals	Week 10 Follow-up/Final visit for withdrawals	Week 10 Follow-up/ Final visit for withdrawals	70	EOT+1	No upper limit
AISRS, CGI	Baseline	Baseline	Baseline	1	No Lower limit	1
	Week 2	Week 2 D8	Week 2	8	2	21
	Week 6	Week 6 D40	Week 6	40	35	EOT
	Week 10 Follow-up/ Final visit for withdrawals	Week 10 Follow-up/Final visit for withdrawals	Week 10 Follow-up/ Final visit for withdrawals	70	EOT+1	No upper limit
Pharmacodynamics: SD-ASC**, MEQ- 30**, VAS***	Week 1 D1	Week 1 D1	Week 1 D1	1	NA	5
	Week 6	Week 6 D40	Week 6	40	NA	No upper limit

\* Relative to Study Day 1

\*\*No baseline assessment, post-dose at Week 1 D1

#No assessment at Week 6, only at visit Week1 D1 post-dose

**Table 3: Scheduled Visit Window and Mapping of Assessments for Vital Sign, C-SSRS**

Scheduled Visit Number	Scheduled Time point	Label on output	Target Study Day*	Time Interval Lower Limit (Day*)	Time Interval Upper Limit (Day*)
Baseline	Baseline	Baseline - Week 1 D1	1	No Lower limit	1
Week 1 D5	Week 1 D5	Week 1 D5	5	2	6
Week 2 D8	Week 2 D8	Week 2 D8	8	7	10
Week 2 D12	Week 2 D12	Week 2 D12	12	11	13
Week 3 D15	Week 3 D15	Week 3 D15	15	14	17

Scheduled Visit Number	Scheduled Time point	Label on output	Target Study Day*	Time Interval Lower Limit (Day*)	Time Interval Upper Limit (Day*)
Week 3 D19	Week 3 D19	Week 3 D19	19	18	20
Week 4 D22	Week 4 D22	Week 4 D22	22	21	24
Week 4 D26	Week 4 D26	Week 4 D26	26	25	27
Week 5 D29	Week 5 D29	Week 5 D29	29	28	31
Week 5 D33	Week 5 D33	Week 5 D33	33	32	34
Week 6 D36	Week 6 D36	Week 6 D36	36	35	38
Week 6 D40	Week 6 D40	Week 6 D40	40	39	EOT
Week 10 Follow-up/Final visit for withdrawals	Week 10 Follow-up/Final visit for withdrawals	Week 10 Follow-up/ Final visit for withdrawals	70	EOT+1	No upper limit

\*Relative to Study Day 1

**Table 4: Scheduled Visit Window and Mapping of Assessments for daily diary (Sleep Quality)**

Scheduled Visit Number	Scheduled Time point	Label on output	Target Study Day*	Time Interval Lower Limit (Day*)	Time Interval Upper Limit (Day*)
Baseline	Baseline	Baseline	NA	No Lower limit	-1
Week 1	Day 1- Week 1 D5	Week 1	NA	1	6
Week 2	Week 2 D8- Week 2 D12	Week 2	NA	7	13
Week 3	Week 3 D15- Week 3 D19	Week 3	NA	14	20
Week 4	Week 4 D22- Week 4 D26	Week 4	NA	21	27
Week 5	Week 5 D29- Week 5 D33	Week 5	NA	28	34
Week 6	Week 6 D36- Week 6 D40	Week 6	NA	35	EOT
Week 10 Follow-up/Final visit for withdrawals	Week 10 Follow-up/Final visit for withdrawals	Week 10 Follow-up/ Final visit for withdrawals	NA	EOT+1	No upper limit

\*Relative to Study Day 1; NA=Not Applicable

## 2.2 STUDY DOCUMENTS

The following study documents are used for the preparation of the SAP:

- MMED-007 Protocol, final version 5.0, 10 February, 2022;
- Annotated Case Report Form (CRF), version 5.0, 15 August, 2022 (MMED007 DMOP Attachment B Annotated CRF v5.0).

## 2.3 STUDY DATABASES

The following study databases are used in the study:

- CRF database is used in the study;
- Randomization list.
- Final list with concomitant medications, including flags for intake or change in prohibited medications/therapies which have potential confounding effects.

## 3 ASSIGNMENT OF PREFERRED TERMS TO ORIGINAL TERMINOLOGY

The original terms used by investigators to describe medical history and concomitant diseases, physical examination abnormalities, adverse events (AEs), indications for previous/concomitant medications will be associated with preferred terms for classification and tabulation.

The latest MedDRA dictionary will be used for assigning preferred terms. Previous and concomitant therapy will be coded according to ATC.

## 4 REQUIREMENTS FOR SAP EXECUTION

The SAP is executed after:

1. The investigator CRF database is locked;
2. Subject visits are completed and clean;
3. The protocol violation database is locked;
4. The coding database is completed and signed off.

## 5 RESPONSIBILITIES

The Project Statistician will be responsible for selection of the statistical methods. The Statistical Programmer will perform the statistical programming (selected listings, summary tables, analysis tables, figures, and exploratory investigations, as appropriate).

## 6 SOFTWARE FOR STATISTICAL ANALYSIS

The statistical analysis will be carried out by using SAS® version 9.4 – [REDACTED]

## 7 OBJECTIVES

### 7.1 PRIMARY OBJECTIVE

To assess the treatment efficacy vs placebo of repeated low doses (20 µg) of MM-120 for six weeks in adult subjects with ADHD measured by Adult Attention Deficit Investigator Symptom Rating Scale (AISRS).

### 7.2 SECONDARY OBJECTIVES

- To assess treatment efficacy vs placebo measured by change from baseline in AISRS after 1 week (2 doses) of treatment.

- To assess treatment efficacy vs placebo based on the proportion of subjects who experience at least a 1-point decrease in the Clinical Global Impression - Severity of Illness Scale (CGI-S).
- To assess treatment efficacy vs placebo measured by change from baseline in CGI-S.
- To assess other efficacy endpoints by the Adult ADHD Self-Report Scale (ASRS) and Connors' Adult ADHD Rating Scale
- To assess the pharmacokinetic (PK) profile of MM-120 in subjects with ADHD.
- To explore the pharmacokinetic/pharmacodynamic (PK/PD) relationship of single doses of MM-120 and psychological and physiological effects.
- To assess the safety and tolerability by AE and SAE assessment.

### 7.3 Exploratory Objective

To explore sleep quality/ duration as recorded in the daily diary.

For the purpose of future exploratory analysis (not covered in this SAP), for subjects who consent to provide a pharmacogenomics (PGX) sample, a single blood sample (2.5 mL) in a proprietary integrated standardized system for collection and stabilization of specimens (bio banking) will be collected during the study and stored.

## 8 VARIABLES/ENDPOINTS AND DEFINITIONS

### 8.1 SUBJECT CHARACTERISTICS

#### 8.1.1 Demographic characteristics

Demographic characteristics of the subjects include age at screening, sex at birth (male | female) at screening, profession, highest education level (less than primary, primary, secondary, tertiary [bachelor, master, doctoral degree]) and country. Demographics data are derived from “Demographic Characteristics” CRF section.

#### 8.1.2 Baseline disease characteristics

Baseline disease characteristics of the subjects include baseline values for the Adult Attention Deficit Investigator Symptom Rating Scale (AISRS), Clinical Global Impression - Severity of Illness Scale (CGI-S), Adult ADHD Self-Report Scale (ASRS) and Connors' adult ADHD rating scale self-report long form (CAARS-L-SR).

These data are reported on the “AISRS”, “CGI-S” and “Subject Reported Outcomes” CRF sections.

Baseline definition is available in section 11.1.1.

### 8.2 PHYSICAL EXAMINATION AT BASELINE

Physical examination at Baseline includes height (cm), weight (kg), body mass index (BMI, kg/m^2), blood pressure (mmHg), heart rate (bpm) and an assessment of the following: general appearance, skin, head and neck, lymph nodes, thyroid, abdomen, musculoskeletal, cardiovascular, respiratory, and neurological systems.

### 8.3 MEDICAL HISTORY AND CONCOMITANT DISEASES

Medical history and concomitant diseases are collected in the “Prior Medical and Psychiatric Events” CRF section.

Subject medical history pertains to any previous Disease/Disorder/Surgery/Procedure (i.e. conditions in the form with the box ‘ongoing’ not ticked); concomitant diseases are any of the above condition with the box ‘ongoing’ ticked.

The original terms used by the investigators to describe Disease/ Disorder/ Surgery/ Procedure will be coded with the MedDRA v25.1.

Previous conditions will be reported separately from concomitant diseases.

### 8.3.1 ADHD Medical history

Attention-deficit/hyperactivity disorder (ADHD) medical history is available in the "ADHD Medical History" CRF section and the following characteristics are of interest:

- Time since ADHD diagnosis (in accordance with the rules, described in Section 11.2);
- Structured interview to assess diagnostic criteria according to DSMV [All criteria met (all criteria must be met for a diagnosis of ADHD in adults) | Not all criteria met];
- Complete CAARS-S-OR observer rating screening [(Yes|No). If Yes, then show: (A, B, C, D) scores];
- Current somatic disorder(s) [(Yes|No). If Yes, disease/disorder will be specified under specific SOC/PT of AEs summary];
- Previous hospitalisation(s), previous disorders, (somatic and psychiatric), previous surgery(s) [(Yes|No). If Yes, If Yes, disease/disorder will be specified under specific SOC of Medical History summary];
- Family History (psychiatric and somatic) [Yes|No];
- ADHD medication (prescription or non-prescription) [(Yes|No). If Yes, then show in separate summary table: (Name of medication/therapy, Indication, Total daily dose, Unit, Amount taken in the morning, Amount taken in the afternoon, Amount taken in the night time, Date of last dose)];
- Alcohol, caffeine, nicotine:
  - Current smoker [(Yes|No). If Yes, then show: (Cigarettes per day, Packs per year)];
  - Coffee [(Yes|No). If Yes, then show: (Coffee per day)];
  - Alcohol (Beer, wine, liquor etc. (standard drink)) [(Yes|No). If Yes, then show: (Per week)];
- MDMA/Ecstasy [(Yes|No). If Yes, then show: (Total lifetime use, Last use (dd.mm.yyyy))];
- Sedative, Narcotic (Benzos, Ketamine, Laughing gas (nitrous oxide)) [(Yes|No). If Yes, then show: (Total lifetime use, Last use (dd.mm.yyyy))];
- Hallucinogenic (LSD, Mescaline, Psilocybin) [(Yes|No). If Yes, then show: (Total lifetime use, Last use (dd.mm.yyyy))];
- Stimulants (Amphetamine, Cocaine, Methylphenidate (recreationally)) [(Yes|No). If Yes, then show: (Total lifetime use, Last use (dd.mm.yyyy))];
- Opioids (Morphine, Diacetylmorphin, Codeine, Methadone) [(Yes|No). If Yes, then show: (Total lifetime use, Last use (dd.mm.yyyy))];
- Cannabis, Marijuana, CBD [(Yes|No). If Yes, then show: (Total lifetime use, Last use (dd.mm.yyyy))];
- Others: (GHB, PCP, DXM, Spice) [(Yes|No). If Yes, then show: (Total lifetime use, Last use (dd.mm.yyyy))];

### 8.4 PREVIOUS AND CONCOMITANT MEDICATIONS

Previous and concomitant medications are collected in the "Concomitant Medications" CRF section. Medications for ADHD are those medications with the response "Yes" to the question 'Is this medication for ADHD?'.

Missing/Partial dates will be imputed according Section 11.3.3.

#### **8.4.1 Previous medications**

Any treatment with the stop date before the study treatment start date (see definition in Section 11.1.1).

#### **8.4.2 Concomitant medications during treatment period**

Any treatment taken during the treatment period (Section 11.1.1). This includes any treatment with:

- The start date on or after the treatment start date and before study treatment end date (included)

OR

- The start date before the treatment start date AND the stop date after or on the study treatment start date

Handling of missing dates is defined in section 11.3.3.

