13.5 Prior and Concomitant Medication

Prior medication is defined as any medication taken before the date of the first dose of randomized treatment. Concomitant medication is defined as any medication taken on or after the date of the first dose of randomized treatment.

Both prior and concomitant medication use will be summarized by the number and proportion of subjects in each treatment group receiving each medication within each therapeutic class for the SAF.

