#### **8.4.3 Prohibited concomitant medications.**

Any treatment that may interfere with the IMP taken during the study. This includes treatment from Day -1/Baseline (Visit 2) until End of Study or Early Termination (except if needed for care and treatment of the subject during the study per Investigator discretion).

The **Error! Reference source not found.** in APPENDIX C provides a listing of prohibited medications; however, it is not a comprehensive list of all restricted medications, supplements, and other therapeutics. Final list with prohibited medications will be identified on a case-by-case basis by a Sponsor medical review of the concomitant medications.

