### 10.3.4 Previous and concomitant medications

Individual subject listing will be provided on the FAS.

Previous and concomitant medications (Section 8.4) will be summarized displaying counts and percentages of subjects having taken at least one treatment. A specific summary for previous and concomitant ADHD medication will be provided.

Counts and percentages of subjects having taken at least one treatment will be presented by Anatomic Therapeutic Chemical (ATC) class 3 and individual preferred term within each ATC as well as by individual preferred term. The summary tables will be presented in descending order according to their incidence in the active treatment group (e.g., ATC and individual preferred term within each ATC with the highest number of occurrences appear first) sorting ties alphabetically.

The counting of the medications will be handled as follows:

- Subjects who took more than once the same medication (as qualified by its preferred term(s)) will be counted only once;
- In case the reported medication is assigned to several preferred terms, subjects will be counted for each individual preferred term.

Prohibited medications will be flagged in the listing with the concomitant medications and will be summarized separately as defined for concomitant medications above. Final list with prohibited medications will be provided by the Sponsor.

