### **11.1.1.3 Study treatment end date (EOT)**

This is the last day of study drug intake, which is the date reported in “Date of visit” field in section “Medical Events checks” (for each Visit form) when “LSD / Placebo administered” is ticked “Yes” in “Study Drug Administration” section.

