### **11.1.1.5 Treatment period**

It is the period from the start date to the end date (limits included) of study treatment administration.

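### SAP 8.4.2 ends concomitant medication at the last dose, against Protocol 13.5, so drugs started later can drop out of tables CM and CMADHD

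*SAP*

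**What the plan says.** **Protocol 13.5.** "Concomitant medication is defined as any medication taken on or after the date of the first dose of randomized treatment". No end date is given.

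**SAP 8.4.1, previous.** "Any treatment with the stop date before the study treatment start date".

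**SAP 8.4.2, concomitant during the treatment period.** There are two routes in. The first is by start date: "The start date on or after the treatment start date and before study treatment end date (included"). The second is for drugs already running: "The start date before the treatment start date AND the stop date after or on the study treatment start date".

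**SAP 11.1.1.3 and 11.1.1.5.** The study treatment end date is defined by "This is the last day of study drug intake". Of the treatment period the SAP says: "It is the period from the start date to the end date (limits included) of study treatment administration".

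**SAP 8.4.3, prohibited.** This category has its own, longer window: "This includes treatment from Day -1/Baseline (Visit 2) until End of Study or Early Termination". It exempts drugs needed for the subject's care at the Investigator's discretion. The final list comes from a Sponsor medical review of the concomitant medications. SAP Appendix C lists ADHD stimulants and non-stimulants.

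**SAP 10.3.4 and 12.2.4.** Table CM summarises concomitant medication, CMADHD concomitant ADHD medication, and PT concomitant prohibited medication. Prohibited drugs "will be flagged in the listing with the concomitant medications and will be summarized separately as defined for concomitant medications above".

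**SAP Table 8.** A medication whose stop date is missing is treated as concomitant, and the date is not replaced.

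**SAP Appendix D.** Item 12 changes how confounding medications are handled. No item mentions the end of the concomitant window.

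**The concern.** The SAP replaces an open-ended protocol definition with one that closes at the last dose, and does not declare the change. SAP 8.4.1 and 8.4.2 then leave a gap: a drug that begins after the last dose did not stop before Day 1, did not start by the last dose, and was not running at first dose.

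The follow-up period is a plausible time for subjects to begin other treatment, including ADHD treatment. Adverse events are tabulated through that period: SAP 10.12.1.1 has a column of non-dosing days that runs from the last dose to end of study or early termination. A reader of those tables would look to CM and CMADHD to see what else subjects were taking, and could find too few entries.

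What is at stake is the completeness of two descriptive tables and the context for adverse events after the last dose.

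**Working it through.** The plan gives no figure to reproduce. The check applies the date rules as written.

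**Inputs**
- First dose on Day 1; last scheduled dose on Day 40 (SAP 8.6).
- Week 10 visit, target Day 70 (SAP Table 2).
- For a subject who stops early, an assumed last dose on Day 15 with follow-up to Day 70. Day 15 is a scheduled dosing day; the choice is an illustration.

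**Rules**
- Previous (SAP 8.4.1): stop < 1.
- Concomitant (SAP 8.4.2): 1 ≤ start ≤ last dose, or start < 1 and stop ≥ 1.
- Prohibited (SAP 8.4.3): on the prohibited list and taken at some time from Day -1 to end of study or early termination.
- Concomitant (Protocol 13.5): stop ≥ 1.

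**Examples for a completer, stop date recorded**

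| Start, stop | Not prohibited: SAP | Prohibited: SAP | Protocol |
|---|---|---|---|
| Day -20, Day -5 | previous | previous | prior |
| Day 5, Day 8 | concomitant | concomitant and prohibited | concomitant |
| Day 40, Day 43 | concomitant | concomitant and prohibited | concomitant |
| Day 41, Day 50 | none | prohibited only | concomitant |
| Day 50, Day 70 | none | prohibited only | concomitant |

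**All start and stop pairs from Day -30 to Day 70.** For a drug that is not prohibited, 465 pairs have no SAP category, and all of them start on Days 41 to 70. That is every pair with such a start: 30 + 29 + … + 1 = 30 × 31 / 2 = 465. For a drug falling under 8.4.3, no pair is without a category.

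**Length of the gap**
- Completer: 70 − 40 = 30 start days; 30/70 = 43%.
- Assumed stop on Day 15: 70 − 15 = 55 start days; 55/70 = 79%. It is shorter if an early-termination visit soon follows the last dose.
- With the window carried to end of study or early termination: 0 in both cases.

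With 26 subjects per arm, each subject left out of a table is 1/26 = 3.8 percentage points of that arm.

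**The same drug, two answers.** Take an ADHD drug started on Day 45. With a stop date of Day 55 it fails both routes in 8.4.2 and is absent from CM and CMADHD. With a missing stop date, Table 8 makes it concomitant. The classification turns on whether a stop date was recorded.

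**Table PT.** SAP 8.4.3 runs to end of study or early termination. However, 10.3.4 refers back to the treatment of concomitant medications, and the table's title calls the drugs concomitant. If that carries over the 8.4.2 window, prohibited drugs started after the last dose drop out of PT. If it carries over only counting rules and layout, they stay. The text does not say which.

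**The case against.** The heading of 8.4.2 says openly that it concerns the treatment period, and 8.4.3 supplies a longer window for the drugs that matter most. That answers several stronger readings that a reader might take from the gap.

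- *ADHD and other prohibited drugs started after the last dose have no category and disappear from the summaries.* Not supported. SAP 8.4.3 covers them to end of study or early termination, Appendix C includes ADHD drugs, and 10.3.4 gives them a listing flag and table PT. The text that 10.3.4 refers back to gives counts, ATC class, sorting and counting rules, with no date window, so layout is the more natural reading.
- *Switches between the last dose and Week 6 escape the intercurrent-event flag.* Not supported. SAP 10.7.2.1.1 points to 8.4.3, not 8.4.2, and its fallback rule for missing assessment dates accepts event start dates up to Day 44, past the scheduled last dose.
- *Week 10 efficacy would be misread.* The SAP specifies no Week 10 efficacy summary. AISRS and CGI-S are summarised at Weeks 2 and 6, ASRS and CAARS-L-SR at Weeks 2, 4 and 6. For completers the Week 6 AISRS is taken before the final dose.

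Table 8 also limits the loss, since a drug with no stop date is counted. Listing LM shows start and stop dates and a prohibited flag, if it is built from every record in the Concomitant Medications CRF section.

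All of this stands. It does not remove the conflict between 8.4.2 and Protocol 13.5, the missing entry in Appendix D, or the literal effect on CM and CMADHD.

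**Conclusion.** The point holds and is minor. SAP 8.4.2 contradicts Protocol 13.5 without declaring it. Read literally, it omits from CM and CMADHD any drug first started after the last dose with a recorded stop date. For a completer on schedule the affected starts are Days 41 to 70 (30 of 70 days, 43%). How many subjects this concerns cannot be told from the documents.

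Drugs that are not prohibited then have no category at all. Prohibited drugs keep one through 8.4.3, apart from those exempted as needed for care, which would also have none. Whether table PT uses the longer window is unclear, which is not the same as showing that it loses entries.

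The primary and key secondary analyses are not shown to be affected. The consequence is limited to descriptive medication counts and the context for adverse events after the last dose. This assumes dosing on the SAP schedule, follow-up to Day 70, and a programmer who applies 8.4.1, 8.4.2 and Table 8 as written.

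**What to change.** 1. Align SAP 8.4.2 with Protocol 13.5: any medication taken on or after first dose, through end of study or early termination. If wished, show drugs started after the last dose separately in CM and CMADHD.
2. State in 8.4.3 and 10.3.4 that table PT and the Sponsor's review use the 8.4.3 window, Day -1 to end of study or early termination.
3. If the narrower window is intended, keep it but record it in Appendix D, name a category for drugs started after the last dose, and make Table 8 agree, so that a missing stop date does not change the classification.

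The cost is SAP wording and, if the split is chosen, one extra column in each of two tables. No new data are needed: concomitant medication is already recorded through the Week 10 or early-termination visit.
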